3.6 DATA HANDLING & CONFIDENTIALITY

Following consent, participants will be referenced by their participant ID number (e.g. MLR001). Their e-mail address will be recorded next to their participant ID number, gender, role (i.e. doctor or nurse) and training grade, on an Excel spreadsheet for the purpose of contacting participants as the study progresses. The participant's hospital of work will not be recorded. Once their commitment to the study has been ended, the e-mail address will be deleted. The Excel spreadsheet will be kept on a password protected laptop computer. Non-identifiable data will be backed up with secure storage for a period of 10 years for purpose of reference to data requested regarding any research published.

Video recordings from the SPEs will be transferred from the recording device to a password protected USB stick referenced by the participant ID followed by SPE1 (baseline) or SPE2 (post-intervention), e.g. MLR001_SPE1. Once the independent reviewer has viewed the video and marked

the participant, the video file will be destroyed. Audio recordings from the interviews will be transcribed by the CI and PageSix Transcription Services (we have a confidentiality agreement in place with PageSix). Transcripts will be identified by the participant study number and saved to the password protected computer. Once transcripts have been checked for accuracy, the original audio files will be destroyed.

Physical files (i.e. consent forms) will be kept in a security locked office in [name].

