3.5 MEASURES

Questionnaires

Once consent is gained, the participants will complete a baseline (pre-intervention) questionnaire (appendix 4) reporting their demographics, previous exposure to breaking bad news training and their engagement with mobile learning resources. The questionnaires will be printed and available for completion following consent. If participants would rather have more time to complete the questionnaire, an electronic version will be sent via e-mail for them to complete and return within two weeks.

The post-intervention questionnaire (appendix 5) will be offered at the time of the second SPE (four to six weeks following randomisation). If any participants wish to not attend the SPE, the post-intervention questionnaire will still be offered to them. Participants will be given two weeks to complete and return the questionnaire.

The questionnaires utilise a five-point Likert scale (37,38) ranking of the user's confidence and agreeability with statements. Some statements have a white space to write comments. The questionnaires are novel to this study and were developed using principles of Kirkpatrick's Model of Learning Evaluation (39), the Theory of Planned Behaviour (40) and the Technology Acceptance Model (41), whilst also drawing on the most important curricula competencies derived from the content analysis of a sample of medical and nursing curricula followed by an expert consensus (unpublished work by CI).

Simulated patient encounters

SPEs allow assessments of skills in a safe and controlled environment, without impacting patient care (42). Participants will be asked to complete two SPEs – the first at baseline, and the second four to six weeks post-intervention. The CI will send dates for the candidates to choose the best time for the SPE. The participants will have to ensure the time taken for the assessments are outside their clinical commitments or they have adequate clinical cover if they are participating during work hours. Those working within the same department will be encouraged to participate on the same day to avoid discussion within the group of participants who have and have not completed the SPE. The SPEs will be arranged within the hospital premises where the participants work or within the premises of the Academic Surgical Unit at Imperial College London.

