Prior to the start of the SPE, the participant will be given a participant task sheet to read, which summarises the task (appendix 6A and an example in appendix 6B). They will be reminded that their personal performance scores will remain confidential (not distributed beyond the CI and his co-investigators). They will be offered the opportunity to have the consultation documented as a work-based assessment for their portfolio.

The participant will be given 15 minutes to conduct a consultation with a SP where they have to break bad news. The SP will be role-played by a professional actor/patient known to Clinical Skills team within the Department of Surgery and Cancer, from a bank of professional actors/patients who have experience in communication skills training and have previously been trained to participate in SPEs. The actor/patient will be compensated for their time according to their agreement with the department. A short introduction to their character and how they may respond to questions and ques will be provided (appendix 7A and an example in appendix 7B). Task and character sheets are adapted from templates provided by MockOSCE (43). Separate scenarios will be used at baseline and post-intervention. The previously validated Breaking bad news Assessment Schedule (BAS) (36) will be used as the mark sheet (appendix 8) to quantify participant interaction with the SP. The BAS has been shown to have high internal consistency (Cronbach's alpha score of 0.93) and the interrater reliability was within the moderate to good range (weighted kappa values 0.4510, 0.6817 and 0.6114) (36). The mark-sheet will be completed by the SP and the CI at the time of the SPE. The encounter will be video-recorded so that it can be viewed by the independent assessor at a later date to complete the mark sheet. Therefore, three separate assessor scores will be used when calculating the overall performance score of each participant.

Following the completion of the SPE, the participant will be reminded not to discuss the scenario with other members of their department who have not yet completed the consultation. Following the completion of the second SPE and the post-intervention questionnaire, the participants will have no further commitments to the study.

Semi-structured interviews

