Appendix 8 Simulated patient encounter: BAS Mark Sheet

BAS Mark Sheet v2.1 (18/03/2019)

Mobile learning resources as a tool for improving clinician's ability to break bad news: A pre-post mixed methods pilot study

(IRAS ID 258886)

Participant ID:

Title: Breaking bad news to [insert brief title]

Time allowed: 15 minutes

Assessor (select one): Researcher / Simulated patient / Independent marker

Breaking bad news Assessment Schedule (BAS)

When marking please place a circle round the number which reflects the score you wish to give. The points adjacent to each question are for guidance only.

A. Setting the scene			
This section looks at whether the participant facilitated an initial rapport before breaking the bad			
news. This can be done by providing an environment which allows private and comfortable			
communication, by the participant introducing him/herself, and by the participant showing an			
interest in the patient as an individual.			
1.	Did the participant arrange the	The participant may have	
	environment?	 placed the chairs at an angle which allowed eye contact? 	
		 ensured that the desk was not in-between him/her and 	
	verv well 5 4 3 2 1 poorly	the patient?	
	-, ,	 prepared for the patient becoming upset, for example by 	
		placing the tissues so the patient could reach them?	
		• taken measures to prevent interruptions?	
2.	Did the participant use an	The participant may have	
	appropriate greeting and	• stood up to greet the patient?	
	introduction?	• established the patient's name?	
		Introduced him/herself using his/her own hame? given a brief description of his/her occupation?	
	definitely 5 _ 4 _ 3 _ 2 _ 1 not at all	• shown the nationt where to sit?	
		• shown the patient where to sit:	
3.	Did the participant show interest	The participant may have	
	in the patient's current state of	 used open questions? 	
	well-being and personal	 established recent events for the patient? 	
	circumstances at the beginning of	 established the patient's physical state? 	
	the interview?	 asked how the patient felt emotionally? 	
		• enquired into the patient's social circumstances?	
	definitely 5 4 3 2 1 not at all	• given the patient time to finish their statements?	
B. B	reaking the news	1	
This section specifically focuses on whether the participant was sensitive to this patient's			
1	This section specifically rocuses on whether the participant was sensitive to this patient s		

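### No rater of the simulated encounters is masked to time point, not even the video assessor, and the allocation of scenarios to time points is not stated

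*Combined protocol and SAP*

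**What the plan says.** Each simulated patient encounter is scored on the 23-item Breaking bad news Assessment Schedule (BAS) by three raters, and all three scores feed the overall performance score (3.5).

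- **Live raters.** "The mark-sheet will be completed by the SP and the CI at the time of the SPE". The chief investigator also arranges the sessions: "The CI will send dates for the candidates to choose the best time for the SPE".
- **Video rater.** The recording is to be "viewed by the independent assessor at a later date to complete the mark sheet".
- **Labelling.** Section 3.6 has the files "referenced by the participant ID followed by SPE1 (baseline) or SPE2 (post-intervention". It describes no re-coding and no viewing order. "Once the independent reviewer has viewed the video and marked" the participant, the file is destroyed.
- **Scenarios.** "Separate scenarios will be used at baseline and post-intervention". Appendices 6 and 7 hold templates and one example, not tied to a time point.
- **Mark sheet (Appendix 8).** The header has the participant ID, the scenario title and a rater field, "Assessor (select one): Researcher / Simulated patient / Independent marker". It has no time-point field. Item 16 is scored against the concerns on the character sheet.
- **Analysis.** Section 7.2 compares baseline and post-intervention scores by a paired t-test at p < 0.05. Section 7.1 states that there is no comparator group.

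**The concern.** The hypothesis in 1.3 is directional: the resource improves ability. A rater who knows that a clip is the second encounter may expect it to be better and mark accordingly. The chief investigator knows the time point. The simulated patient may infer it, although no section says that this person is told. The independent assessor is the one rater for whom masking is practical, and none is described.

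The scenario question is tied to this. If one scenario always comes first, renaming the files will not mask the assessor, because the mark sheet carries the scenario title and item 16 needs the character sheet. Any difference in difficulty would then also be inseparable from the effect of the resource, for all three raters.

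Without a comparator group, either shift passes undiluted into the estimated change, and no planned analysis would reveal it. Section 7.2 does plan second coding against analysis bias for the qualitative data, but describes no equivalent for the BAS marks.

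**Working it through.** The plan has no figure to reproduce: 7.1 gives no effect size, SD or power. The calculation below only shows scale.

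**From the documents.** n = 15 to 20 (study summary; 20 in 7.1); paired t-test at 0.05 (7.2); 23 items scored 1 to 5, so a total of 23 × 1 = 23 to 23 × 5 = 115 (Appendix 8); three raters.

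**Assumed.** Two-sided test; equal rater weights; SD of paired differences 12 (varied from 10 to 20); rater bias of 0.1, 0.2 or 0.3 point on 20 items, leaving out items 15 to 17 as anchored to content; no bias in the simulated patient; true effect zero.

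**Method.** Noncentral t with n − 1 degrees of freedom and noncentrality (shift / SD) × √n. The result is the two-sided rejection rate, nominally 5%.

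**Rater bias.** On one rater's total the bias is 20 × 0.1, 0.2 or 0.3 = 2, 4 or 6 points. In the three-rater mean, one biased rater contributes a third of this (0.67, 1.33, 2.00) and two contribute two thirds (1.33, 2.67, 4.00).

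| Biased raters | n = 20 | n = 15 | Range, SD 10–20 and n 15–20 |
|---|---|---|---|
| Video assessor only | 5.6 / 7.6 / 10.9% | 5.5 / 6.9 / 9.2% | 5.2–13.6% |
| Chief investigator and assessor | 7.6 / 15.7 / 29.4% | 6.9 / 12.6 / 22.5% | 5.7–39.7% |

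If both are biased, masking the assessor brings the second row back to the first. The bias of the live rater stays.

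**Scenario gap, fixed order only.** A gap of 2, 4 or 6 points on the total affects all raters, so it enters in full: 10.9 / 29.4 / 56.5% at n = 20 and 9.2 / 22.5 / 43.8% at n = 15. These rates hold for a gap in either direction. An easier second scenario mimics improvement; a harder one hides it.

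**Balanced order.** Half the participants gain d and half lose d, so the mean shift is zero. The SD, if order is not modelled, becomes √(144 + d²) = 12.2, 12.6 or 13.4 for d = 2, 4 or 6.

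**Precision of the assessor's score alone.** The half-width of the 95% confidence interval is t(0.975, n − 1) × SD / √n. For the three-rater mean this is 2.093 × 12 / √20 = 5.6 and 2.145 × 12 / √15 = 6.7 points. For one rater the SD grows by 1 / √((1 + 2r) / 3), with r the between-rater correlation. Taking the lowest and highest kappas cited in 3.5 as r (an assumption), r = 0.4510 gives 1.256 and r = 0.6817 gives 1.127. The half-widths are then 6.3 to 7.1 points (n = 20) and 7.5 to 8.4 (n = 15).

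**The case against.** The strongest reply is that the argument rests on silences. Section 3.6 sets a storage label; it does not say that the assessor sees it. Fixed scenario order is not stated either, and Figure 1 could not be read. This is fair: the documents establish that no masking or allocation is described, not that bias will occur. But nothing in the text prevents either problem, and neither can be repaired once clips have been marked and destroyed.

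Second, the magnitudes are all assumed, and the largest belong to the scenario question, not to masking. Both points stand. For the assessor alone the inflation is small at the low end.

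Third, 3.5 already encourages colleagues from one department to attend on the same day, to limit discussion. A scenario that nobody meets before the second visit supports that safeguard, and balancing the order weakens it. This is a real trade-off. It is eased by assigning the order by department or session, so that colleagues attending together meet the same scenario.

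Fourth, masking one rater of three leaves the planned test exposed, and the masked score is noisier. Its precision may also be worse than shown, because the kappas describe agreement on single scores, not on changes: at r = 0.2 the half-width at n = 20 would be about 8.2 points. That is a reason to report the masked score as a sensitivity result and not to let it decide the conclusion.

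**Conclusion.** The concern holds as a cheap improvement. That no masking and no scenario allocation are described is a matter of text and is certain. How large the resulting bias would be cannot be derived from the documents. Under the assumptions above, masking the assessor addresses an inflation from 5% to at most 13.6%. Balancing the order addresses a shift that could be much larger, but exists only if the planned order is fixed and the scenarios differ in difficulty. Neither step removes practice effects or bias in the live raters. The exploratory label in 7.1 lowers the stakes but does not remove the point, since the plan still states a directional hypothesis and a significance threshold.

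**What to change.** - **3.6:** Give each clip a random code that does not show the time point, with the key held by someone other than the independent assessor. Use that code in place of the participant ID on the assessor's mark sheet. Have the assessor mark all clips in random order after the last second encounter, and destroy them afterwards.
- **3.5:** State how scenarios are allocated, and balance their order across time points within doctors and within nurses, by department or session where possible. The present safeguard is that "the participant will be reminded not to discuss the scenario with other members of their department" who have not yet completed it; extend this until colleagues have completed both encounters.
- **7.2:** Report the masked assessor's mean BAS change with a 95% confidence interval beside the three-rater result, as a sensitivity result without veto. Acknowledge that the live raters are unmasked.

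**Cost.** A code key and an order list, using the existing raters. The downsides are:

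- Clips are held longer. If the last recruit joins on 30 June 2019 and the second encounter follows six weeks later (11 August), a clip from 1 January is held 222 days and one from 18 March, the version date, 146 days. A further two-week delay before the first encounter (an assumption) would make this 25 August, 236 and 160 days. The extra time over the current plan is unknown, since 3.5 fixes no marking date. The participant information should be checked for what it says on retention.
- Marking falls late: 15 to 20 participants × 2 clips × 15 minutes = 7.5 to 10 hours, in a study due to finish by August.
- Both scenarios circulate from baseline, so discussion between colleagues matters more.
- Balanced order adds a little spread unless order is allowed for in the analysis.
- Coding hides neither the pairing of clips nor every cue within them.

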3.7 RISKS

There are no foreseeable physical harms associated with this research. Some participants and the professional actors/patients may become emotional during the SPEs. They will be treated with dignity, respect and dealt with sensitively. If participants or professional actors/patients become overly distressed during the SPEs, it will be abandoned, and support offered, initially by the CI and if required the Occupational Health service for their institution. Alternatively, they will be asked to seek support from their General Practitioner.

4. PARTICIPANT ENTRY

4.1 PRE-REGISTRATION EVALUATION

None.

4.2 INCLUSION CRITERIA

- Working and training within NHS England and Bupa Cromwell Hospital.
- Junior doctor, pre-certificate of completion of training (of any specialty).
- Junior nurse band 5 to 6 (any specialty).
- Over the age of 18.
- Able to communicate and write in English.
- Willing to engage with mobile learning resources as an additional task to their clinical role, ensuring their learning does not take time out of their clinical commitments.

4.3 EXCLUSION CRITERIA

- Medical and nursing students.
- Clinicians who have completed their training programmes i.e. medical or nursing consultants, matrons.
- Retired clinicians.

4.4 WITHDRAWAL CRITERIA

Participants can choose to stop participating in the study before or during the study, without giving a reason, by informing the CI. The SPEs can be stopped at any time by informing the assessors. Following completion of the study, the participant can decide to withdraw from the study up to two weeks after without giving a reason by informing the CI.

5. ADVERSE EFFECTS

5.1 DEFINITIONS

Adverse Event (AE): any untoward medical occurrence in a patient or clinical study subject.

Serious Adverse Event (SAE): any untoward and unexpected medical occurrence or effect that:

- Results in death.
- Is life-threatening refers to an event in which the subject was at risk of death at the time of the event; it does not refer to an event which hypothetically might have caused death if it were more severe.
- Requires hospitalisation, or prolongation of existing inpatient's hospitalisation.
- Results in persistent or significant disability or incapacity.
- Is a congenital anomaly or birth defect.

Medical judgement should be exercised in deciding whether an AE is serious in other situations. Important AEs that are not immediately life-threatening or do not result in death or hospitalisation but may jeopardise the subject or may require intervention to prevent one of the other outcomes listed in the definition above, should also be considered serious.

5.2 REPORTING PROCEDURES

All adverse events should be reported. Depending on the nature of the event the reporting procedures below should be followed. Any questions concerning adverse event reporting should be directed to the CI in the first instance.

Given the nature of this study, it is not anticipated that any AEs or SAEs will occur.

However, any SAEs should be reported to the Imperial College Research Ethics Committee where in the opinion of the CI, the event was:

- 'related', i.e. resulted from the administration of any of the research procedures; and
- 'unexpected', i.e. an event that is not listed in the protocol as an expected occurrence.

Reports of related and unexpected SAEs should be submitted within 15 days of the CI becoming aware of the event, using the NRES SAE form for non-IMP studies. The CI must also notify the Sponsor of all SAEs.

6. ASSESSMENT & FOLLOW-UP

Following the completion of their semi-structured interview, the participant will have no further commitments to the study. The study is intended to commence in January 2019 with final recruitment to be at the end of June 2019, to complete the study by August 2019. Following this, there will be no follow-up of the participants unless they have chosen to receive a summary of the results, in which case this will be e-mailed to them.

7. STATISTICS & DATA ANALYSIS

7.1 SAMPLE SIZE

Due to the exploratory nature of this educational pilot study, the sample size will be relatively small, especially as all participants will be given the intervention and there are no comparator groups. Considering that there are two professional groups involved (doctors and nurses) a sample of ten participants from each (20 in total) should be sufficient to answer the research question and allow for thematic analysis of the post-intervention interview transcripts.

Schildmann et al. and similar studies either did not formally report on or had low attrition rates as their interventions were part of the participant's training (44). This makes it difficult to estimate the level of attrition in our study, especially as the intervention is not mandatory for training. However, it is estimated that attrition levels will be low as evidenced by similar studies.

7.2 DATA ANALYSIS

Data will be analysed at Imperial College London.

The SPE will be marked by three assessors: the CI, the SP and an independent assessor. The marks are in the form of a numerical scale (appendix 8) for quantitative analysis. The scores will be recorded on an Excel spreadsheet against the participant ID. Each participant will act as their own control, with their baseline and post-intervention scores being compared. Using IBM[®] SPSS Statistics Software, a paired sample t-test will be used to statistically analyse the results (with p < 0.05 considered a statistically significant change).

The baseline and post-intervention questionnaires will be analysed by the CI using a combination of a spreadsheet for the quantitative elements (converting the Likert scale into a numerical scale), and qualitative data management software (i.e. NVivo from QRS International) for the white space answers.

The user's confidence in breaking bad news at baseline and post-intervention will be self-assessed on a Likert scale which will be converted to a numerical scale:

- Confidence five-point scale: Not very confident at all (= 0); not very confident (= 1); somewhat confident (= 2); very confident (= 3); extremely confident (= 4).
- Agreeability five-point scale: Strongly disagree (= 0); disagree (= 1); neutral (= 2); agree (= 3); strongly agree (= 4).

Each participant will act as their own control, with comparisons drawn from their own Likert scale ratings from baseline and post-intervention. A paired sample t-test will be used to statistically analyse the results as above.

The answers to open ended questions will be transcribed into a Word file and then uploaded onto NVivo for thematic analysis. This will be performed by the CI becoming familiar with the content of the transcriptions and then thematically coded and analysed. To counter analysis bias, a selection will be reviewed and coded by a second researcher, with any disagreement resolved through discussion. The second researcher will not have access to personal data and will only view anonymised transcripts.

The semi-structured interviews will be transcribed verbatim either by the CI or PageSix Transcription Services and analysed by the CI using NVivo (qualitative data management software). Thematic analysis will be performed by the CI by becoming familiar with the content of the transcriptions

followed by thematic coding and analysis. To counter analysis bias, a selection will be reviewed and coded by a second researcher, with any disagreement resolved through discussion. The second researcher will not have access to personal data and will only view anonymised files.

